9.3.1.1 Time to Death through in-patient hospital stay (including ICU stay)

Time to death during in-patient hospital stay will be calculated as [(date of death due to any cause) – randomization date] for those subjects who died in hospital prior to hospital discharge visit without prior liver transplant. Subjects who are alive and active in the study at their discharge date will be censored at their discharge date. Subjects who discontinue prior to their discharge visit without having death will be

censored at their last contact date or discharge date (whichever is earlier). A subject who has not been discharged before the end of study will be censored at their last contact day. A subject who had liver transplant will be censored at the last contact date, or discharge date or liver transplant date (whichever is earlier). The endpoint will be analyzed in ITT population.

9.3.1.2 Time to transplant or death through in-patient hospital stay (including ICU stay)

The time to death or liver transplant through in-patient hospital stay will be calculated as [(the date of liver transplantation or the date of death during in-patient hospitalization, whichever is first) – randomization date] for those subjects who died or had liver transplant in hospital prior to hospital discharge visit. Subjects who are alive without liver transplant and active in the study at their discharge date will be censored at their discharge date. Subjects who discontinue prior to their discharge visit without having death and liver transplant will be censored at their last contact date or discharge date (whichever is earlier). A subject who has not been discharged before the end of study will be censored at their last contact day. The endpoint will be analyzed in ITT population.

9.3.1.3 Time to liver transplant or death through Day 28 after randomization

Time to 28-day transplant-free survival will be calculated as [(the earlier of liver transplantation or death) – randomization date] for those who died or had liver transplant on or prior to 28 days. Subjects who neither died nor had a liver transplant within the cut-off date will have their time to event censored at the earlier of the following times:

- Date of last contact.
- Cut-off date (i.e. 28 days) for analysis.

The endpoint will be analyzed in ITT population.

9.3.1.4 Time to hospital discharge

Time to hospital discharge will be calculated as [discharge date -randomization date). Subjects who had a liver transplant or death during the hospitalization will be censored to the earliest date of liver transplant or death. Subjects who haven't been discharged before the end of study and have not had a liver transplant or death will be censored to their last contact date. The endpoint will be analyzed in ITT population.

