The number and percentage of subjects showing a specific ACLF course (resolution, improvement, steady course, or worsening) or a specific organ failure as well as the number and percentage of new infections at the end of hospitalization will be compared between treatment groups by means of Fisher’s exact or Chi-square test. As sensitivity analyses, treatment effects will be adjusted for clinically and statistically significant imbalances in baseline characteristics by fitting appropriate Logistic Regression model or by means of the Cochran-Mantel-Haenszel (CMH) test.

Time-to-hospital discharge will be estimated by the Kaplan-Meier method and compared between treatment groups by the Log-rank test stratified by region and the 3 ACLF grades.

Albumin level in serum will listed for each subject and summarized by treatment group.

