9.2 Determination of Sample Size

Based on the results from the CANONIC study, the overall 90-day mortality rate is assumed to be about 50% in the whole study population ([13,22](#)). Assuming a potential drop-out rate of 10% and 5% type-1 error for a 2-sided Chi-square test, a global sample size of 380 subjects (190 per treatment group) will allow 80% statistical power to detect an absolute reduction of 15% (a 35% 90-day mortality rate) in subjects treated with SMT+PE-A 5%.

Alternatively, the sample size was calculated based on the log-rank test as follows. Assuming the 90-day mortality rate is 50% for the control group, or equivalently, the survival rate is

GRIFOLS
 
Bioscience Industrial Group
	Number	BIG-CL-PRT-000002	Version	6.0	Status	Retired	Effective Date	29-Mar-2023
	IG1407 - Effects of Plasma Exchange with Human Serum Albumin 5% (PE-A 5%) on Short-term Survival in Subjects with "Acute-On-Chronic Liver Failure" (ACLF) at High Risk of Hospital Mortality							Page
								78 of 102

50%, which translates to a hazard rate of 0.0077 assuming an exponential distribution. Using a log-rank test at the two-sided significance level of 5%, a total of 141 events would provide at least 80% power to detect an absolute reduction of 15% in mortality rate (a 35% 90-day mortality rate, or equivalently, a 65% survival rate) in subjects treated with SMT + PE-A 5%. This absolute difference in mortality rates translates to a hazard ratio of 0.6215, or an approximate 38% risk reduction. With all subjects followed for the entire 90-day duration of the study, a total of 332 subjects would be required to obtain 141 events. Assuming a dropout rate of 10%, a global sample size of 370 subjects (185 per treatment group) is required. This sample size calculation was performed using Proc Power with the “Twosamplesurvival” statement in SAS version 9.4.

Taking a conservative approach, the larger of the 2 sample sizes (ie, the one based on the Chi-square test) will be used to ensure the study has sufficient power.

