9.3 Level of Significance to Be Used

All statistical tests will be 2-sided and the significance level will be fixed at 0.05.

More details including approaches for multiplicity adjustments (if needed) will be provided in the SAP.

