9.3.1 Exploratory Time to Event Endpoints after Randomization

The following endpoints will be analyzed using the same methodology as the primary analysis for the primary endpoint described in section 9.1.2.

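### The in-hospital and discharge endpoints censor competing events, so their planned Kaplan-Meier probabilities and medians overstate how many patients are discharged and how many die in hospital

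*SAP*

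**What the plan says.** SAP 9.3.1.4 (time to hospital discharge): "Subjects who had a liver transplant or death during the hospitalization will be censored to the earliest date of liver transplant or death".

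SAP 9.3.1.1 (in-hospital death): "Subjects who are alive and active in the study at their discharge date will be censored at their discharge date". A transplanted subject is also censored there, at the transplant date if that comes first.

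SAP 9.3.1.2 (in-hospital transplant or death): "Subjects who are alive without liver transplant and active in the study at their discharge date will be censored at their discharge date".

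SAP 9.3.1 sends all of these to one set of methods: "The following endpoints will be analyzed using the same methodology as the primary analysis for the primary endpoint". Those methods, in SAP 9.1.2, are a stratified Cox model, Kaplan-Meier medians and quartiles, Kaplan-Meier probabilities at Day 28 and Day 90 with confidence intervals, and a stratified log-rank test. They also include the number and percentage of subjects with and without the event.

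Protocol 9.1.2.4 plans the same: "Time-to-hospital discharge will be estimated by the Kaplan-Meier method and compared between treatment groups by the Log-rank test", with the in-hospital endpoints handled like the primary endpoint. Neither document mentions competing risks or cumulative incidence, and none of the sensitivity analyses in SAP 9.1.3, 9.2.3 or 9.3.11 deals with them.

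**The concern.** A patient who dies in hospital can never be discharged, and a patient who has gone home can no longer die during that stay. Censoring one event while estimating the other treats these patients as if they were still waiting for it. The Kaplan-Meier complement then describes a hypothetical ward from which the other exit has been removed. It is not the proportion of patients who left alive or who died in hospital.

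The plan would print these values as Day 28 and Day 90 probabilities and as medians, and readers will take them as patient proportions. In a population with high short-term mortality the gap is not small. The tests have a related limit. A log-rank test with the competing event censored compares cause-specific hazards, which is a different question from whether more patients get home or fewer die in hospital.

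**Working it through.** **Inputs.**
- Death: 34% by Day 28, the CANONIC 28-day mortality for ACLF-1b/2/3a at diagnosis (Protocol Table 2-2). It is a proxy for in-hospital death and is varied over 20-40%.
- Discharge alive: not given in the documents. Assumed 45% by Day 28, varied over 30-55%.
- Treatment effect on death: the plan's hazard ratio. Protocol 9.2 says "the overall 90-day mortality rate is assumed to be about 50% in the whole study population" and takes 35% under treatment. This reproduces as ln(0.65)/ln(0.50) = 0.6215, as stated. The documents give no design figure for the three endpoints at issue.
- Constant hazards, used for size only.

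**Formulas.** Let a be the daily hazard of death and b that of discharge. With D and R the proportions dead and discharged by Day 28:
- a + b = -ln(1 - D - R)/28, split in the ratio D:R
- planned value for death: 1 - KM = 1 - exp(-a·t)
- actual proportion (cumulative incidence): [a/(a + b)]·[1 - exp(-(a + b)·t)]
- for discharge, exchange a and b.

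**Central case.** a + b = -ln(0.21)/28 = 0.0557, so a = 0.0240 and b = 0.0317.

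| | Day 28, 1 - KM | Day 28, actual | Day 90, 1 - KM | Day 90, actual |
|---|---|---|---|---|
| In-hospital death | 48.9% | 34.0% | 88.5% | 42.8% |
| Discharge alive | 58.9% | 45.0% | 94.3% | 56.6% |
| Sum | 107.8% | 79.0% | 182.7% | 99.3% |

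Two exclusive outcomes cannot add to more than 100%; the Kaplan-Meier figures do.

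**Medians.** The Kaplan-Meier median to in-hospital death would be ln 2/0.0240 = 28.9 days. Yet the proportion dying in hospital never exceeds a/(a + b) = 0.43, so no such median exists.

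**Range.** Over the nine combinations of D (20, 34, 40%) and R (30, 45, 55%), the extremes are:
- D = 20%, R = 30%: death 24.2% against 20.0%, discharge 34.0% against 30.0% at Day 28; Day 90 sum 133%.
- D = 40%, R = 55%: death 71.7% against 40.0%, discharge 82.3% against 55.0% at Day 28; Day 90 sum 198%.

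The Day 28 overstatement is thus about 4 to 32 points for death and 4 to 27 points for discharge.

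**What the discharge test sees.** Take the central case as control, multiply the death hazard by 0.6215 and leave the discharge hazard unchanged. Actual discharge alive by Day 90 rises from 56.6% to 67.0%. Both Kaplan-Meier discharge curves still read 94.3%, because b is the same. In 4,000 simulated trials of 380 subjects (unstratified, two-sided 5%), the discharge log-rank rejects in about 5% and a cumulative-incidence comparison in about 40%.

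**The case against.** The best defence has four parts.

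- **Crude percentages are already planned.** SAP 9.1.2 tabulates subjects with and without events. By Day 90 few patients remain in hospital (0.7% in the central case), so these counts come close to the true Day 90 proportions. This stands, but it gives no correct Day 28 figure, median, curve or comparison, and the Kaplan-Meier values would sit beside it uncorrected.
- **The tests are valid for what they test.** This stands. A reader might infer that the log-rank can invent an effect. The documents do not support that: with no difference between arms the simulated rejection rate stays near 5%. Adding a discharge hazard ratio of 0.7 to the death effect leaves Day 90 discharge nearly equal (56.6% against 57.7%) and the log-rank rejects in 74%, but discharge really is slower there. A second simulated case, rejecting in 11.1% with no effect on death times, needs mixed-risk patients and an 8-day discharge delay that no document gives.
- **The missed discharge gain is not hidden overall.** In that same scenario the planned in-hospital death curves differ, at 88.5% against 73.9% by Day 90. Read together, the planned endpoints show the effect.
- **Cumulative incidence can mislead too.** If plasma exchange only slows discharge (hazard ratio 0.7, no effect on the death hazard), in-hospital deaths rise from 42.8% to 51.1% through longer stay alone. Sessions can run to Day 16, so a delay is plausible. This is a good reason to keep the cause-specific results rather than discard them.

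**Conclusion.** The concern holds for the estimates. The planned Kaplan-Meier probabilities and medians for SAP 9.3.1.1, 9.3.1.2 and 9.3.1.4 are wrong as statements about how many patients are discharged or die in hospital. The direction does not depend on the assumptions: whenever competing events occur, one minus Kaplan-Meier exceeds the cumulative incidence. The in-hospital survival probability is correspondingly understated, not overstated. The size does depend on the assumed discharge rates, the mortality proxy and constant hazards, and the ranges above should be quoted with those conditions. The figures were worked for death and discharge; the composite in 9.3.1.2 has the same structure but was not computed separately.

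A reader might go further and infer that the trial's main conclusions are at risk. They are not. The three endpoints are exploratory and outside the fixed testing sequence of SAP 6.5. The primary and secondary survival endpoints are not censored at discharge, and the sample size of 380 does not rest on these analyses. The subgroup versions (SAP 9.3.1.5) carry the same estimation problem but report no p-values.

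**What to change.** For SAP 9.3.1.1, 9.3.1.2 and 9.3.1.4:

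1. Replace the Kaplan-Meier probabilities and medians with Aalen-Johansen cumulative incidence by arm at Day 28 and Day 90, with confidence intervals.
2. Compare arms by a Gray test stratified by region and ACLF grade, or by a Fine-Gray model.
3. Name the competing events: discharge alive and transplant for in-hospital death (9.3.1.1); discharge alive for transplant or death (9.3.1.2); death and transplant for discharge (9.3.1.4). The last then estimates discharge alive without prior transplant and should be labelled so, since a transplanted patient may still go home.
4. Keep the stratified log-rank and Cox results, label them cause-specific, and interpret the discharge and in-hospital death results together.
5. Record the change in SAP section 12 or, if the SAP can no longer be amended, as a documented additional analysis in the clinical study report.

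The dates of death, transplant and discharge are already used by the SAP, so no new data are needed and standard SAS procedures suffice. The cost is a few extra outputs and a departure from Protocol 9.1.2.4 that must be described and justified under Protocol 9.6. The last patient visit has already taken place (SAP section 2), so the change should be described openly as a late one.

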9.3.1.5 Exploratory Subgroup Analysis (Exploratory Endpoints)

The primary analysis will be repeated for each ACLF subgroup (ACLF-1B, ACLF-2, or ACLF-3a) and region (Europe vs NA) All subgroup analyses will be performed using the ITT population.

In each defined subgroup category, the analysis will be carried out using the same methodology described in section [9.1.2](#) and the hazard ratio and CI for the subgroup will be estimated. When the subgroup is defined by a stratification factor used for the randomization, the stratification factor will not be used in the stratified Cox PH model. For example, in the analysis of ACLF subgroup, only region will be used as the stratification factor in the stratified Cox PH model. These results are considered exploratory, due to both multiplicity concerns and small sample sizes that cannot be pre-specified. Only summary statistics and CIs will be presented; p-values will not be determined. A minimum of 30 subjects must be present in each subgroup category for the analysis to be performed.

The subgroup analysis will be applied to primary, secondary and exploratory endpoint time to event endpoints after randomization.

9.3.2 CLIF-C OF Score and Sub Scores for Organ Function

CLIF-C OF scores evaluated at baseline (last measurement taken prior to treatment day 1), during and after the treatment period, and at the end of hospitalization (or before liver transplantation or death) will be listed.

The CLIF-C OF score system consists of six sub-scores for liver, kidney, brain, coagulation, circulatory, and respiratory organs/systems - each with values of 1, 2 or 3 with a higher number representing more severe disease.

Each CLIF-C OF sub-score will be summarized as a categorical variable by treatment for each visit. The CLIF-C OF sub-scores will be compared at visits when the data are collected for both treatment groups using the generalized linear models implemented in SAS GENMOD procedure, in which the CLIF-C OF sub-score is modeled by the proportional odds cumulative logit model for ordinal data with adjustment for baseline sub-score, region (Europe of North America) and ACLF subgroup (ACLF-1B, ACLF-2, or ACLF-3a) treatment, visit and treatment-by-visit interaction, as independent variables), and the robust variance estimate for the treatment effect will be estimated based on the independent working correlation structure.

The total CLIF-C OF score is a discrete numeric value in the range of 6 to 18 (inclusive) and is defined as the sum of the six organ/system sub-scores. If an individual sub-score is missing, the total score will also be missing. The total CLIF-C OF score and change in total score from baseline to each scheduled post-baseline visit will be summarized, as a continuous variable, by treatment and scheduled visit, excluding visits that follow liver transplantation. In addition, the total score change from baseline for scheduled visits with data for both treatment groups will be analyzed by MMRM, which includes change from baseline as the dependent variable; treatment, visit, region (Europe of North America) and ACLF subgroup (ACLF-1B, ACLF-2, or ACLF-3a), treatment-by-visit interaction, region-by-visit interaction, and ACLF subgroup (ACLF-1B, ACLF-2, or ACLF-3a)-by-visit interaction as fixed effects; baseline and baseline-by-visit as covariates; and measures within-subject at each visit as a repeated measure. The model employs an unstructured covariance matrix for the within-subject dependence. The treatment effect will be evaluated using the full model, with no backward or stepwise selection methods. If the model fails to converge, the mixed effects model with a compound symmetry correlation structure will be used.

Assessments after Liver transplant will be removed from summaries and analysis.

9.3.3 CLIF-C ACLF Score

The CLIF-C Acute-on-Chronic Liver Failure (ACLF) score is a continuous numeric value in the range of 0-100 with a higher number representing more severe disease, derived from the CLIF-C OF total score, and is defined as:

$$\text{CLIF-C ACLF} = 10 * [0.33 * \text{CLIF-C OFs} + 0.04 * \text{Age \{years collected on the demographics eCRF page\}} + 0.63 * \text{Ln}(\text{white cell count \{10}^9 \text{ cells/L\}}) - 2]$$

The CLIF-C ACLF score will be included in the listing of CLIF-C OF scores and will be summarized as a continuous variable. The total score and change in total score from baseline (last measurement taken prior to the start of study treatment for SMT+PE 5% group and last measurement on or prior to the randomization date for SMT alone) to each post-baseline scheduled visit will be summarized by treatment and each visit. In addition, the MMRM analysis of CLIF-C OF scores will be repeated for change from baseline CLIF ACLF total score.

Assessments after Liver transplant will be removed from summaries and analysis.

9.3.4 MELD Score

The Model for End-stage Liver Disease (MELD) score is a continuous numeric value in the range of 6-40, with a higher number representing more severe disease, and is defined as:

$$\text{MELD} = 9.57 \cdot \ln(\text{Creatinine \{mg/dl\}}) + 3.78 \cdot \ln(\text{Bilirubin \{mg/dl\}}) + 11.2 \cdot \ln(\text{INR}) + 6.43$$

If any of the individual clinical parameters used to derive the MELD score report results <1, the result is imputed to 1. For creatine reported >4, the result is imputed to 4(8). These parameters are then used to derive the MELD score. Any final MELD score >40 will be rounded to 40. MELD scores are evaluated monthly through Month 12 and will be listed.

The MELD score will be summarized as a continuous variable. The MELD total score and change in total score from baseline ((last measurement taken prior to the start of study treatment for SMT+PE 5% group and last measurement prior to randomization date for SMT alone) to each scheduled post-baseline visit will be summarized, as a continuous variable, by treatment and scheduled visit. In addition, the MMRM analysis of CLIF-C OF scores will be repeated for the change from baseline total scores.

Assessments after Liver transplant will be removed from summaries and analysis.

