5.2 Exclusion Criteria

A subject meeting any of the following exclusion criteria is NOT eligible for participation in the study.

1. Subjects without ACLF.
2. Subjects with ACLF-1a or ACLF-3b (See [Table 2-1](#) for ACLF grades) after the Screening Period.
3. Subjects fulfilling inclusion criteria that improve to no ACLF or to ACLF-1a or worsen to ACLF-3b during the Screening Period (between initial evaluation and time of randomization).
4. Subjects with ACLF for more than 10 days prior to randomization.
5. Subjects with acute or subacute liver failure without underlying cirrhosis.
- 6v3 Subjects with septic shock requiring use of norepinephrine (> 0.3 mcg/kg/min) or need for a second vasopressor (including terlipressin).
- 7v3 Subjects with active bacterial or fungal infection: who have received less than 24h of appropriate antibiotic treatment.
- 8v3 Subjects with severe respiratory failure with PaO2/FiO2 ≤200.
9. Subjects with active or recent bleeding (unless controlled for >48 hours).
10. Subjects with severe thrombocytopenia (≤20×10⁹/L) (based on local laboratory assessment).
11. Subjects with chronic renal failure and currently receiving hemodialysis.

GRIFOLS
 
Bioscience Industrial Group
	Number IG1407 - Effects of Plasma Exchange with Human Serum Albumin 5% (PE-A 5%) on Short-term Survival in Subjects with "Acute-On-Chronic Liver Failure" (ACLF) at High Risk of Hospital Mortality	BIG-CL-PRT-000002	Version 6.0	Status	Retired	Effective Date	29-Mar-2023
						Page	47 of 102

12. Evidence of current locally advanced or metastatic malignancy. Subjects with hepatocellular carcinoma within the Milan criteria (1 nodule ≤ 5 cm or 3 nodules ≤ 3 cm [[Appendix 5](#)]), non-melanocytic skin cancer, and controlled breast or prostate cancer, can be included).
13. Subjects with severe chronic heart failure (New York Heart Association [NYHA] class III or IV) ([Appendix 6](#)).
14. Subjects with severe pulmonary disease (Global Obstructive Lung Disease [GOLD] stage III or IV) ([Appendix 7](#)).
15. Subjects with severe myopathy as defined clinically.
16. Subjects with a known infection with human immunodeficiency virus (HIV) or have clinical signs and symptoms consistent with current HIV infection.

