7 ASSESSMENT OF EFFICACY

7.1 Efficacy Variables

Definitions

Diagnosis of cirrhosis will be established by histology or by clinical, analytical, and ultrasonographic findings. Organ failures will be defined according to the CANONIC Study criteria ([Table 2-1](#)). Liver failure: serum bilirubin ≥12.0 mg/dL; kidney failure: serum creatinine level ≥2.0 mg/dL or renal-replacement therapy; coagulation failure: International Normalized Ratio ≥2.5; cerebral failure: grade III or IV HE according to the West-Heaven criteria ([Appendix 9](#)) ([49](#)); circulatory failure: use of any vasopressor to maintain hemodynamic stability (the use of terlipressin for the treatment of HRS is not included in this definition); and respiratory failure: ratio of partial pressure of arterial oxygen to fraction of inspired oxygen (FIO₂) ≤200 or pulse oximetric saturation to FIO₂ ratio ≤214. Kidney dysfunction will be defined by a serum creatinine level ranging from 1.5 to 1.9 mg/dL. Mild-to-moderate HE will be defined by grade I or II HE.

ACLF-1a will be diagnosed in subjects with single kidney failure. ACLF-1b will be diagnosed in subjects with single organ failure with serum creatinine between 1.5 and 1.9 mg/dL and/or HE grade 1-2; ACLF-2 in the presence of 2 organ failures; and ACLF-3a in the presence of 3 organ failures, and ACLF-3b in the presence of 4 or more organ failures ([Table 2-1](#)). Complete response will be defined as resolution of ACLF or improvement to ACLF-1a and partial response as a reduction of 1 organ failure or more to ACLF-1b or ACLF-2.

Septic shock will be diagnosed in the presence of circulatory failure associated with inadequate oxygen utilization by the cells/inadequate tissue perfusion requiring vasopressor drugs. The presence of hypotension, although commonly present (MAP less than 60 to 65 mmHg), will not be required to define shock ([50](#)). Refractory septic shock will be diagnosed in subjects with high vasopressor requirements (norepinephrine dose >0.5 mcg/kg/min) ([51](#)). Diagnosis of ARDS will be established on the basis of a ratio PaO₂/FiO₂ ≤300 or a pulse oximetric saturation (SpO₂) to FiO₂ ratio ≤357 ([52](#)) add in the presence of bilateral lung infiltrates and normal left ventricular function.

Illness Severity Scores

The CLIF-C OF score, CLIF-C ACLF score, Child-Pugh score, and MELD score (Appendix 4) will be used to assess the clinical condition severity of the subjects.

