Appendix 4 Criteria to Define Organ Failure (CLIF-C OF Score)

CLIF-Organ Failure score system.			
Organ / System	Sub-score = 1	Sub-score = 2	SUB-Score = 3
Liver	Bilirubin <6mg/dL	6 ≤ Bilirubin <12mg/dL	Bilirubin ≥12mg/dL
Kidney	Creatinine <2mg/dL	2 ≤ Creatinine <3.5 mg/dL	Creatinine ≥3.5 mg/dL or renal replacement
Brain (West-Haven grade for HE*)	Grade 0	Grade 1-2	Grade 3-4
Coagulation	INR <2.0	2.0 ≤ INR <2.5	INR ≥2.5
Circulatory	MAP ≥70 mm/Hg	MAP <70 mm/Hg	Use of vasopressors
Respiratory PaO ₂ /FiO ₂ or SpO ₂ /FiO ₂	>300 >357	≤300 - >200 >214- ≤357	≤200 (#) ≤214 (#)

The shaded area describes criteria for diagnosing organ failures; *HE: Hepatic Encephalopathy; # patients enrolled in the study with MV were considered as presenting respiratory failure (respiratory sub-score=3) except for patients intubated due to severe HE or to other reasons and not to a respiratory failure, in whom respiratory failure is defined according to the PaO₂/FiO₂ ratio.# Other patients enrolled in the study with MV were considered as presenting a respiratory failure (respiratory sub-score=3).

CLIF-C ACLF Score

CLIF-C ACLFs = 10*[0.33*CLIF-C OFs + 0.04*Age {years} + 0.63*Ln(white cell count {10⁹ cells/L}) - 2]

Child-Pugh Score

Child-Turcotte-Pugh Classification for Severity of Cirrhosis			
	Points*		
	1	2	3
Encephalopathy	None	Grade 1-2 (or precipitant induced)	Grade 3-4 (or chronic)
Ascites	None	Mild to moderate (diuretic responsive)	Severe (diuretic refractory)
Bilirubin (mg/dL)	< 2	2-3	>3
Albumin (g/dL)	> 3.5	2.8-3.5	<2.8
INR	<1.7	1.7-2.3	>2.3
*Child-Turcotte-Pugh Class obtained by adding score for each parameter (total points)			
Class A = 5 to 6 points (least severe liver disease)			
Class B = 7 to 9 points (moderately severe liver disease)			
Class C = 10 to 15 points (most severe liver disease)			

MELD Score

MELD Score = 9.57 Ln(Creatinine {mg/dl}) + 3.78 Ln(Bilirubin {mg/dl}) + 11.2 Ln(INR) + 6.43

GRIFOLS
 
Bioscience Industrial Group
	
Number
 
BIG-CL-PRT-000002
 
IG1407 - Effects of Plasma Exchange with Human Serum Albumin 5% (PE-A 5%) on Short-term Survival in Subjects with "Acute-On-Chronic Liver Failure" (ACLF) at High Risk of Hospital Mortality
	
Version
 
6.0
	
Status
 
Retired
	
Effective Date
 
29-Mar-2023
	
Page
 
95 of 102

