Appendix 4 – Illness Severity Score Details

CLIF-Organ Failure score system.			
Organ / System	Sub-score = 1	Sub-score = 2	SUB-Score = 3
Liver	Bilirubin <6mg/dL	6 ≤ Bilirubin <12mg/dL	Bilirubin ≥12mg/dL
Kidney	Creatinine <2mg/dL	2 ≤ Creatinine <3.5 mg/dL	Creatinine ≥3.5 mg/dL or renal replacement
Brain (West-Haven grade for HE*)	Grade 0	Grade 1-2	Grade 3-4
Coagulation	INR <2.0	2.0 ≤ INR <2.5	INR ≥2.5
Circulatory	MAP ≥70 mm/Hg	MAP <70 mm/Hg	Use of vasopressors
Respiratory			
PaO ₂ /FiO ₂	>300	≤300 - >200	≤200 (#)
or			
SpO ₂ /FiO ₂	>357	>214 - ≤357	≤214 (#)

*The shaded area describes criteria for diagnosing organ failures; *HE: Hepatic Encephalopathy; # patients enrolled in the study with MV were considered as presenting respiratory failure (respiratory sub-score=3) except for patients intubated due to severe HE or to other reasons and not to a respiratory failure, in whom respiratory failure is defined according to the PaO₂/FiO₂ ratio. # Other patients enrolled in the study with MV were considered as presenting a respiratory failure (respiratory sub-score=3).*

CLIF-C ACLF Score

$$\text{CLIF-C ACLFs} = 10^{*}[0.33^{*}\text{CLIF-C OFs} + 0.04^{*}\text{Age \{years\}} + 0.63^{*}\text{Ln(white cell count \{10}^9 \text{ cells/L\})} - 2]$$

Child-Pugh Score

Child-Turcotte-Pugh Classification for Severity of Cirrhosis			
	Points*		
	1	2	3
Encephalopathy	None	Grade 1-2 (or precipitant induced)	Grade 3-4 (or chronic)
Ascites	None	Mild to moderate (diuretic responsive)	Severe (diuretic refractory)
Bilirubin (mg/dL)	< 2	2-3	>3
Albumin (g/dL)	> 3.5	2.8-3.5	<2.8
INR	<1.7	1.7-2.3	>2.3
*Child-Turcotte-Pugh Class obtained by adding score for each parameter (total points)			
Class A = 5 to 6 points (least severe liver disease)			
Class B = 7 to 9 points (moderately severe liver disease)			
Class C = 10 to 15 points (most severe liver disease)			

MELD Score

$$\text{MELD Score} = 9.57 \text{ Ln(Creatinine \{mg/dl\})} + 3.78 \text{ Ln(Bilirubin \{mg/dl\})} + 11.2 \text{ Ln(INR)} + 6.43$$

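### SAP 9.3.4 puts the reported creatinine into MELD even for subjects on renal replacement therapy, which the plan's other kidney measures override

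*SAP*

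**What the plan says.** SAP 9.3.4 describes MELD as a "continuous numeric value in the range of 6-40, with a higher number representing more severe disease". The formula, also given in Appendix 4 of both documents, is "MELD Score = 9.57 Ln(Creatinine {mg/dl}) + 3.78 Ln(Bilirubin {mg/dl}) + 11.2 Ln(INR) + 6.43". Three adjustments apply:

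- creatinine, bilirubin and INR are each raised to 1 when the reported value is lower;
- high creatinine is truncated: "For creatine reported >4, the result is imputed to 4(8";
- the total is truncated as well: "Any final MELD score >40 will be rounded to 40".

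Each is triggered by a reported number. Neither the section nor the two appendices have a rule for RRT.

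Two other measures in the same documents do. Protocol 7.1 defines "kidney failure: serum creatinine level ≥2.0 mg/dL or renal-replacement therapy". In the CLIF-C OF table (SAP Appendix 4 and protocol Appendix 4), kidney sub-score 3 is "Creatinine ≥3.5 mg/dL or renal replacement".

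RRT can be present at entry, because the only related exclusion is "Subjects with chronic renal failure and currently receiving hemodialysis" (protocol 5.2). It can also be started on study; protocol 6.1.1.2 names it as an option when cardiac overload is treated.

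SAP 9.3.4 compares change in MELD between arms with the MMRM of 9.3.2. It drops assessments after liver transplant but keeps those made on RRT. SAP 7.3 also tabulates baseline MELD.

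**The concern.** Both CLIF-C OF and the kidney-failure definition attach RRT to the creatinine threshold with an *or*. That clause is needed only if a dialysed subject's creatinine can lie below the threshold although the kidney has failed. MELD has no such clause. The same subject at the same visit can therefore hold the worst kidney sub-score and a MELD lowered by the treatment for that failure, although the SAP says a higher MELD means more severe disease.

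Three things are at stake, all within an exploratory endpoint:

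- individual MELD values for subjects on RRT;
- the between-arm MMRM estimate, if RRT use differs by arm in this open-label trial;
- the baseline MELD table and change scores, for subjects already on RRT at entry.

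**Working it through.** **Inputs.** The formula, the floor of 1, the creatinine cap of 4 and the score cap of 40 come from SAP 9.3.4. The pairing of RRT with creatinine 3.5 or above comes from Appendix 4. On-RRT creatinine and RRT rates are not in the documents, so they are assumed and varied.

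**1. The plan's own figure.** With all three inputs at 1, the logarithms vanish and MELD = 6.43. This rounds to 6, the stated lower end of the range. The formula and floor are read correctly.

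**2. Understatement per subject.** Relative to scoring RRT at the SAP's cap, the creatinine term is too low by 9.57 × ln(4/Cr):

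| Measured Cr (mg/dL) | Relative to 4 | Relative to 3.5 |
|---|---|---|
| 3.0 | 2.75 | 1.48 |
| 2.5 | 4.50 | 3.22 |
| 2.0 | 6.63 | 5.36 |
| 1.5 | 9.39 | 8.11 |
| 1.0 | 13.27 | 11.99 |

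The last column uses 3.5, the level that Appendix 4 pairs with RRT. Because of the floor at 1, 13.27 is the maximum.

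**3. A worked subject.** Take bilirubin 12 and INR 2.5. The other terms sum to 3.78 × ln 12 + 11.2 × ln 2.5 + 6.43 = 9.39 + 10.26 + 6.43 = 26.09 (unrounded sum). MELD is 39.35 at creatinine 4 or above, 32.72 at 2.0 and 29.97 at 1.5. If creatinine goes from 4 to 2.0 on RRT, MELD falls by 6.63 while the kidney sub-score stays at 3.

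**4. Where the score cap binds.** Take bilirubin 20 and INR 3. The other terms sum to 11.32 + 12.30 + 6.43 = 30.06 (unrounded sum). Raising creatinine from 1.0 to 4 then adds 40 − 30.06 = 9.94 points, not 13.27. Raising it from 3.0 to 4 adds nothing, because 30.06 + 9.57 × ln 3 = 40.57 is already truncated to 40.

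**5. Change from baseline can also rise.** Take baseline creatinine 1.5 and on-RRT creatinine 2.0, with bilirubin and INR fixed. The change is 9.57 × ln(2.0/1.5) = +2.75. MELD falls only when the on-RRT value is below that subject's own baseline.

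**6. Shift between arms.** Mean shift = (difference in RRT share) × (understatement per subject on RRT). This is before the cap and assumes similar on-RRT creatinine in both arms:

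| RRT difference | Cr 3.0 | Cr 2.0 | Cr 1.5 | Cr 1.0 |
|---|---|---|---|---|
| 5 points | 0.14 | 0.33 | 0.47 | 0.66 |
| 10 points | 0.28 | 0.66 | 0.94 | 1.33 |
| 20 points | 0.55 | 1.33 | 1.88 | 2.65 |

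The shift favours the arm with more RRT. With equal RRT use it is about zero.

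**The case against.** The best case against this has five parts.

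- **RRT lowering creatinine is an outside premise.** The documents give no on-RRT values. If creatinine stays at 4 or above, nothing changes. This stands, and the point is conditional on it. The *or renal replacement* clauses do show that the plan provides for RRT at creatinine below the threshold.
- **A reader might infer that starting dialysis always makes MELD fall.** The documents do not support that. Step 5 shows a subject whose MELD rises on RRT. What holds is that the score is lower than it would be at the cap.
- **The value 4 is a convention, not the truth.** The SAP uses it only to truncate reported values, and Appendix 4 pairs RRT with 3.5 or above. This stands; using 3.5 reduces each figure by 9.57 × ln(4/3.5) = 1.28 points.
- **A reader might infer a bias in favour of PE-A 5%.** The documents do not support that either. They give no RRT rates. The one directional statement, in protocol 2.7, is that plasma exchange reduced renal replacement needs in a randomised trial in acute liver failure. If that carried over, the bias would run against PE-A 5%. Protocol 6.1.1.2 shows that RRT is possible, not that it is common.
- **The reach is small.** MELD is exploratory and outside the fixed-sequence testing in SAP 6.5. Renal deterioration is also reported through the kidney sub-score and the organ-failure tables. This stands as a limit on importance. It does not make the MELD value right.

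**Conclusion.** The gap holds. As written, SAP 9.3.4 can score a dialysed subject as less ill than the plan's other kidney measures do. This is an incorrect derived value, not just a missing detail.

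If RRT lowers measured creatinine, the understatement relative to the SAP's cap is up to 2.8 points at 3.0 mg/dL, 6.6 at 2.0 and 9.4 at 1.5, and less or nothing where the score reaches 40. Baseline MELD is understated in the same way for subjects on RRT at entry, so their change score can err in either direction.

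A between-arm bias needs a difference in RRT use as well. It would be about 0.3 to 1.3 points per 10 percentage points of difference, before the cap, toward the arm with more RRT. Its actual size and direction cannot be known from the documents.

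The survival endpoints, CLIF-C OF, CLIF-C ACLF and Child-Pugh do not use this rule, so the primary and secondary conclusions are untouched.

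**What to change.** Add to SAP 9.3.4 that, for any assessment made while the subject is on RRT, creatinine is set to 4 mg/dL (the existing cap) before MELD is derived. Apply this at baseline and after baseline, in both arms.

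Two definitions must go with it:

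- **Source of RRT status.** Use an eCRF field if there is one. The documents show only the combined kidney item, so otherwise take RRT as present when the kidney sub-score is 3 and creatinine is below 3.5 mg/dL. An RRT case missed at 3.5 or above is understated by at most 1.28 points.
- **Look-back.** State how long before the creatinine sample an RRT session still counts, so that intermittent RRT is handled the same way throughout.

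It would also help to report RRT use by visit and arm beside the MELD table. In the same sentence of 9.3.4, creatine should read creatinine.

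The cost is one sentence, two definitions and a short derivation step. No patient care changes. Some derived MELD values will differ from those recorded at site, so the listing should show both. If MELD has already been analysed, present the revised score as a supplementary analysis and document it in the study report, as SAP section 2 requires for unplanned analyses.
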